8.3.1 Visit 1: Baseline / Trial Fit / Lens order

- Subjects should attend this visit wearing their **spectacle** lenses
- Explanation of the study.
- Sign informed consent form.
- Collect habitual toric lens brand information
 - Brand
 - Power(s)
 - Replacement schedule (daily, 2-week, monthly)
- Anterior ocular health examination (Slit lamp without fluorescein).
- Insert trial toric **LENS A**, evaluate the fit and optimize the prescription if needed.
- [REDACTED]
- [REDACTED]
- Order final **LENS A**.
- Remove **LENS A** and insert trial toric **LENS B**. Evaluate fit and optimize the prescription if needed.
- [REDACTED]
- [REDACTED]
- Order final **LENS B**.

8.3.2 Visit 2: Lens dispensing (Fit LENS A / Evaluate)

- Subjective assessments
 - Handling on insertion (0 -10 scale).
 - [REDACTED]
 - [REDACTED]
 - [REDACTED])
- [REDACTED]
 - [REDACTED]
 - [REDACTED]
 - [REDACTED]
 - [REDACTED] [REDACTED]
 - [REDACTED]
 - [REDACTED] [REDACTED]
 - [REDACTED]

8.3.3 Visit 3: [REDACTED] (Evaluate LENs A)

8.3.4 Visit 3: Lens dispensing (Fit LENS B / Evaluate)

- Subjective assessments
 - Handling on insertion (0 -10 scale).
 - [REDACTED]
 - [REDACTED]
 - [REDACTED]

8.3.5 Visit 4: [REDACTED] (Evaluate LENS B / Study Exit)

9 Adverse Event Reporting

9.1 Adverse Response Definitions

Adverse Event (AE): An AE refers to any untoward medical occurrence (sign, symptom or disease) in a trial subject that does not necessarily have a causal relationship with the study device. AEs may be classified as 'unanticipated adverse device effects,' 'serious AEs,' 'significant AEs,' or 'non-significant AEs,' as defined below.

Classification	Definition
Serious Adverse Event	Those events that are life-threatening, or result in permanent impairment of a body function, or permanent damage to a body structure or necessitate medical (therapeutic) or surgical intervention to preclude permanent impairment of a body function or permanent damage to a body structure.
Unanticipated Adverse Device Effect	Adverse events in a clinical trial that were not previously identified in the protocol in terms of nature, severity, or degree of incidence. An Unanticipated Serious Adverse Device Effect is an unanticipated adverse event that is serious in nature and caused by or associated with the device and is considered reportable.
Significant Adverse Event	Those non-serious adverse events that occur with contact lens usage that are not sight-threatening but are usually symptomatic and may warrant therapeutic management and /or temporary or permanent discontinuation of contact lens wear.
Non-Significant Adverse Events	Those less severe non-serious adverse events that occur with contact lens usage that are not sight-threatening, may or may not be symptomatic and may warrant palliative management, such as ocular lubricants or temporary interruption of contact lens wear.

AE classification, coding (for reporting to the sponsor) and examples are provided in the following table of Contact LENS Adverse Event Classification and Reporting:

Code	Condition	Potential AE Classification	Reporting
01	Presumed infectious corneal ulcer	SERIOUS	
02	Permanent loss of ≥ 2 lines of best spectacle corrected visual acuity (BSCVA)	SERIOUS	
03	Corneal injury that results in permanent opacification within central cornea (6mm)	SERIOUS	
04	Neovascularization within the central 6mm of cornea	SERIOUS	
05	Uveitis or Iritis	SERIOUS	
06	Endophthalmitis	SERIOUS	
07	Hyphema	SERIOUS	
08	Hypopyon	SERIOUS	
09	Persistent epithelial defect	SERIOUS	
00	Other serious event	SERIOUS	
11	Peripheral non-infectious ulcer (outside central 6mm)	SIGNIFICANT	Notify sponsor as soon as possible,

12	Symptomatic corneal infiltrative events	SIGNIFICANT	within 5 working days; IRB reporting as per requirements
13	Superior epithelial arcuate lesions (SEALs) involving epithelial split	SIGNIFICANT	
14	Any temporary loss of ≥ 2 lines BSCVA for ≥ 2 wks	SIGNIFICANT	
15	Corneal staining \geq dense coalescent staining up to 2mm in diameter (i.e. moderate staining)	SIGNIFICANT	
16	Corneal neovascularization \geq 1.0mm to 1.5mm vessel penetration (if 2 Grade change from baseline)	SIGNIFICANT	
17	Any sign and/or symptom for which subject is administered therapeutic treatment or which necessitates discontinuation of lens wear for ≥ 2 weeks	SIGNIFICANT	
10	Other significant event	SIGNIFICANT	
21	Conjunctivitis: bacterial, viral, allergic	NON-SIGNIFICANT	
22	Papillary conjunctivitis if \geq mild scattered papillae/follicles approximately 1mm in diameter (if 2 Grade change from baseline)	NON-SIGNIFICANT	
25	Asymptomatic corneal infiltrative events	NON-SIGNIFICANT	
26	Localized allergic reaction	NON-SIGNIFICANT	
27	Contact dermatitis	NON-SIGNIFICANT	
28	Any sign and/or symptom for which temporary lens discontinuation for > 1 day is recommended	NON-SIGNIFICANT	
20	Other non-significant sign and/or symptom	NON-SIGNIFICANT	

Normal or adaptive symptoms

Transient symptoms such as end-of-day dryness, LENS Awareness, itching or burning or other discomfort may occur with contact lens wear and may occasionally reduce wearing time. **These are not reported as adverse events unless they are unexpected in nature, severity or rate of occurrence.**

9.2 Procedures for Adverse Events

Treatment of an adverse event will depend on its nature and severity. Based on the clinical judgment of the investigator the subject may be referred to an ophthalmologist for treatment. The investigator will attempt to determine whether the reaction is related to the test device or a result of other factors.

An Adverse Event Form will be completed for each adverse event. If both eyes are involved, a separate Adverse Event Form will be completed for each eye. Whenever possible, the adverse event will be photo-documented.

Expenses incurred for medical treatment as part of study participation will be paid by the sponsor (bills and prescription receipts kept). The subject must be followed until resolution and a written report completed indicating the subsequent treatment and resolution of the condition.

9.3 Reporting Adverse Events

All potential **Serious and Unanticipated Adverse Device Effects** that are related or possibly related to subject participation in the investigation will be reported to the Principal Investigator and the sponsor within 24 hours of the investigator becoming aware of the event. The Principal Investigator will report the event to the EC/IRB as soon as possible (by fax, mail/delivery, phone, or email), but within 10 business days of becoming aware of the problem. *All fatal or life threatening events will be reported immediately to the IRB.*

Significant and Non-Significant Adverse Events will be reported to the sponsor as soon as possible, but no later than 5 working days after the occurrence.

9.4 Discontinuation from the Study

All discontinuations will be fully documented on the appropriate CRF Exit and Adverse Event forms as needed. Participants will be followed until resolution (in most instances) and are free of the ophthalmic insert related complications or other ocular pathology. When possible study lenses involved in an Adverse Event will be returned to the sponsor in a new tightly sealed contact lens case, and labeled with the subject identification and stored in Unisol non-preserved saline.

10 Statistical Analysis

[figure not shown]
10.1 Statistical analysis

Summary statistics will be produced, (e.g., mean, standard deviation), by the principal investigator ([name]). Differences between lenses will be compared using Paired t-tests. Paired t-tests /analysis of variance for normal (interval/continuous) data, Wilcoxon's signed ranks test for non-normal (ordinal) data, chi-squares test for nominal data. A Chi-Square test will be used to evaluate lens preference questions. All participants who are evaluated in the study will be used in the analysis. In the event of missing data individual number of points will be excluded in the analysis and not extrapolated from the collected data. The critical alpha level for statistical significance will be set at $p \leq 0.05$, with adjustment for multiple comparisons.

10.2 Sample size

Figure 1 shows the sample size determination for a paired t-test, ($\alpha=0.05$), in order to detect a difference in mean subjective handling scores between lenses. Assuming a standard deviation of 1.2, a sample size of about 37 completed subjects provides 84% power to detect a difference in subjective handling ratings of 0.6 points on a 0 - 10 scale. In order to account for potential subject dropouts or AEs, 10%-15% should be added to the sample size. Therefore, 40 subjects should be enrolled with the aim to complete 37.

Figure 1. Sample size calculation (Minitab 20.2. Statistics software)

Paired t Test

Testing mean paired difference = 0 (versus ≠ 0)

Calculating power for mean paired difference = difference

$\alpha = 0.05$ Assumed standard deviation of paired differences = 1.2

Results

Difference	Sample Size	Target Power	Actual Power
0.6	34	0.80	0.807778
0.6	37	0.84	0.841192
0.6	44	0.90	0.900031

11 Data Quality Assurance

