[figure not shown]
Final

Clinical Evaluation of clariti Monthly Toric and clariti® 1 day Toric

Sponsor Study Code:	EX-MKTG-137
Protocol Date:	June 16, 2022
Sponsor Company:	CooperVision, Inc.
Document Type:	Protocol
Study Category:	Post Market
Start Date:	July 2022
Finish Date:	September 2022
Clinical Site:	School of Optometry Clinic, National Autonomous University (UNAM), Mexico City

Revision History

Document number	Date	Comments
EX-MKTG-137	6/16/2022	First draft (v 1.0)
EX-MKTG-137	6/16/2022	FINAL

Protocol Synopsis

Protocol Number	EX-MKTG-137
Title	Clinical Evaluation of clariti Monthly Toric and clariti® 1 day Multifocal.
Name of Device(s) and (by USAN material)	Clariti Monthly Toric (somofilcon A), clariti 1-Day Toric (somofilcon A)
Indications for Use	
Approved for use:
 
 • somofilcon A. (Daily wear) • somofilcon A. (Daily wear) 
Indication for use in this study:
 
 • 15 minutes daily wear
Study Design	Subject masked, interventional, prospective, direct refit, bilateral wear study.
Purpose	The aim of this non-dispensing fitting study is to evaluate the short term lens fit, vision performance and patient subjective experiences of the Clariti Monthly Toric when compared to the Clariti 1-Day Toric after 15 minutes of daily wear.
Study Duration	
The anticipated timeline for this study is as follows:
 
 • Patient enrolment and completion: July 15 - Sept 15, 2022 Visits: V1: (BL/trial fit/lens order), V2: Dispense / evaluate P1 V3: 15 minutes. Evaluate P1/Dispense P2. V4: 15 minutes. Evaluate P2 / study exit
Patient Population	Habitual soft toric contact lens wearers who provide written informed consent and meet the protocol entrance criteria.
Sample Size	Target enrollment and completion is 37- 40 subjects.
Center Destination (Mexico)	School of Optometry Clinic, National Autonomous University (UNAM)
Number of Centers	Single Center
Patient Follow-up	
Subjects enrolled in this study will be followed up after the lens dispensing session:
 
 • Post dispensing follow-up at 15 minutes for each study lens pair
Primary Endpoint	Subjective handling (insertion & removal)

Table of Contents

1	Introduction	6
2	Study Objective	6
3	Study Hypothesis	6
3.1	Study Hypothesis	6
4	Study Design	7
5	Investigational Sites	7
5.1	Number of Sites	7
5.2	Investigator Recruitment	7
6	Ethics Review / Statement of Compliance	7

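### Enrolling 40 does not provide the plan's own 10%–15% dropout allowance over 37 completers; at that allowance 34–36 complete and power is 81%–83%, not 84%

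*Combined protocol and SAP*

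**What the plan says.** Section 10.2 sizes the study for a paired t-test on subjective handling and reports that "a sample size of about 37 completed subjects provides 84% power". Figure 1 gives the inputs ("Assumed standard deviation of paired differences = 1.2", a difference of 0.6 and a two-sided test at 0.05) and lists sample sizes of 34, 37 and 44 for target powers of 0.80, 0.84 and 0.90.

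To cover dropouts and adverse events, the same section says that "10%-15% should be added to the sample size. Therefore, 40 subjects should be enrolled with the aim to complete 37".

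The Sample Size row of the Protocol Synopsis puts it differently: "Target enrollment and completion is 37- 40 subjects". Section 5.1 repeats 37–40 as the target without saying whether it means enrolled or completed. Neither document section gives any other dropout rate.

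**The concern.** Section 10.2 presents 40 as the result of applying a 10%–15% allowance to 37, but three extra subjects on 37 is less than 10%. The 84% power depends on 37 subjects completing. If attrition is what the plan itself allows for, the enrolment falls short of 37 and the quoted power is not the power the trial would have.

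The Synopsis raises a second, lesser problem. Because one range covers both enrolment and completion, a site working from the Synopsis could enrol 37, leave no margin for dropout, and still be within the stated target.

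Completers are the natural number to look at. A paired comparison needs a rating for both lenses, and Section 10.1 leaves missing values out without imputing them.

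**Working it through.** **Inputs (all from Section 10.2 and Figure 1).** Paired t-test, two-sided, α = 0.05; mean difference 0.6 on a 0–10 scale; SD of paired differences 1.2; 37 completers; 10%–15% to be added; 40 enrolled.

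**Step 1: reproduce the plan's power.** Exact power comes from the noncentral t distribution with n − 1 degrees of freedom and noncentrality (0.6/1.2)·√n = 0.5·√n. The three rows of Figure 1 reproduce to every printed digit:

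| n | Figure 1 | Recomputed |
|---|---|---|
| 34 | 0.807778 | 0.807778 |
| 37 | 0.841192 | 0.841192 |
| 44 | 0.900031 | 0.900031 |

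The power calculation is therefore sound. The difficulty lies only in the step from 37 to 40.

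**Step 2: apply the stated allowance to 37.**

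- Percentage added, n(1 + d): 37 × 1.10 = 40.7 and 37 × 1.15 = 42.55, so 41 to 43.
- Percentage lost from those enrolled, n/(1 − d): 37/0.90 = 41.1 and 37/0.85 = 43.5, so 42 to 44.

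Neither convention gives 40 once rounded up.

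**Step 3: what 40 does allow for.** 40/37 − 1 = 8.1% added; (40 − 37)/40 = 7.5% lost.

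**Step 4: completers and power with 40 enrolled.**

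| Allowance | Completers, 40(1 − d) | Power | Completers if d is read as added, 40/(1 + d) |
|---|---|---|---|
| 7.5% | 37 | 84.1% | – |
| 10% | 36 | 83.1% | 36.4 |
| 15% | 34 | 80.8% | 34.8 |

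Both readings stay below 37 across the stated range. The loss of power against 84.1% is 1.0 percentage point at 10% and 3.3 at 15%. Power at the intermediate value n = 35 is 82.0%.

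**Step 5: the Synopsis read literally.** With 37 enrolled, 37 × 0.90 = 33.3 and 37 × 0.85 = 31.45, so about 33 to 31 complete. Power is 79.5% at n = 33 and 76.9% (0.7685) at n = 31 (truncated and rounded respectively to whole subjects), which is below the lowest target in Figure 1.

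**The case against.** The best reply is that almost nothing turns on this. With 40 enrolled, even a 15% loss leaves 34 completers, and Figure 1 already shows that row at 80.8% power. The plan never calls 84% a required minimum, it says only about 37, and at the low end the gap is between 40.7 and 40. That stands as a judgement of size. It does not make the derivation correct: at 15% the shortfall is 3 to 4 subjects. And although 34/0.85 = 40 exactly, so that 40 would suit the 80% row, the text ties 40 to 37 completers and 84%.

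It can also be said that the plan states an inflation percentage and not an attrition rate, so 34 completers is the harsher reading. That is fair, but the milder reading gives 36.4 to 34.8, still below 37.

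Third, actual loss of primary data may be under 10%. Each lens is worn for 15 minutes, and handling on insertion is rated when each pair is fitted (Sections 8.3.2 and 8.3.4), so someone who leaves after the second insertion rating still contributes a pair. This is plausible. However, the documents give no lower rate, and the Synopsis also names removal in the primary endpoint.

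Finally, the Synopsis range may simply be shorthand for enrolling 40 to complete 37. Section 10.2 says as much, so the scenario with 37 enrolled is secondary. The Synopsis wording nevertheless permits it.

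**Conclusion.** The concern holds. The enrolment of 40 does not follow from the stated 10%–15% allowance: that rule calls for 41–43 or 42–44 depending on convention, while 40 covers an 8.1% addition or a 7.5% loss. At the plan's own allowance, 34–36 subjects complete and power is 80.8%–83.1% instead of 84.1%.

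This is an error in the sample-size justification with a small consequence. It does not make the study seriously underpowered. The power figures rest on the plan's difference of 0.6 and SD of 1.2, and on treating a completer as a subject with both handling ratings. Power falls below 80% only if enrolment stops at 37, which the Synopsis wording allows but Section 10.2 does not intend.

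**What to change.** In Section 10.2, replace the dropout statement with one that matches the figures, for example: *Enrolling 40 allows for a 7.5% loss (37 completers, 84% power); if 10%–15% are lost, 34–36 complete and power is 81%–83%.*

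In the Protocol Synopsis and Section 5.1, replace the single range with two separate targets: *40 enrolled, at least 37 completers targeted.*

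The cost is wording only. No additional enrolment is needed, and the stated power becomes slightly less favourable. If the sponsor prefers to keep both the 10%–15% allowance and 37 completers, the enrolment figure would have to rise to 41–44, depending on the percentage and convention chosen.

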11.1 Study monitoring

A site visit or discussion may be conducted during the course of the study as appropriate. Prior to final data freeze, a close-out visit/discussion may be warranted to check for accuracy and completeness of records. The sponsor or sponsor's representatives will be authorized to gain access to the source documentation for the purposes of monitoring and auditing the study.

11.2 Record keeping

Detailed records of all study visits will be made using the electronic Case Report Forms (CRFs).

11.3 Record retention

Following study completion, data will be available in electronic and/or paper format for audit, sponsor use, or subsequent analysis. The original clinical raw data (including completed CRFs and Informed Consent forms) will be retained according to guidelines set forth in the general work agreement with the site. The Sponsor will be notified and consulted if ever the files are to be destroyed. In the event that this implementation document is indicated for design verification and validation purposes, as indicated on the title page, all original raw data forms and completed CRF's will be forwarded to the sponsor at completion of the final report.

11.4 Data Entry / Data Management

Data will be entered into an electronic spreadsheet. Study staff will only be able to modify the data file via password entry. The investigators will be responsible for the data integrity, and complete data entry for each visit as well as the take home questionnaires. The investigator will send the data collected to the study sponsor within 5 business days after the last subject completes the final visit. A full report will be provided by the investigator at the mutually agreed timeline after the study completion date.

11.6 Publication

The investigators will not be permitted to publish or present at scientific meetings results obtained from the clinical study without prior written consent from the sponsor.

Protocol Amendment

The table below lists the changes to be implemented on this study protocol.

New revision No.	Section (s) to be amended and details.
1.	
The study protocol currently indicates that assessment of subjective comfort will be collected using a 0 -10 visual analog scale with two anchors on each end of the scale.
 
It is recommended to change to a 0 -100 visual analog scale with descriptors at different intervals.
 
The change to be implemented will apply to sections 2.0, 8.3.2, 8.3.3, 8.3.4, and 8.3.5 of the study protocol.

Table 1. Changes to protocol EX-MKTG-137

A large rectangular area of the page is completely blacked out with a thick black marker, obscuring several rows of text that would normally be present in the table body. The redaction is roughly rectangular, covering from approximately [365, 113] to [585, 705].
